5.4.5 Immune Related Toxicity

Blocking CTLA-4 function may permit the emergence of auto-reactive T cells and resultant clinical autoimmunity. Rash/vitiligo, diarrhea/colitis, uveitis/episcleritis, hepatitis, and hypopituitarism were drug-related, presumptive autoimmune events, now termed irAEs, noted in previous ipilimumab studies.

For the purposes of this study, an irAE is defined as an AE of unknown etiology associated with drug exposure and consistent with an immune phenomenon. Efforts should be made to rule out neoplastic, infectious, metabolic, toxin or other etiologic causes prior to labeling an AE an irAE. Serological, immunological, and histological (biopsy) data should be used to support the diagnosis of an immune-mediated toxicity. Suspected irAEs must be documented on an AE or SAE form.

Patients should be informed of and carefully monitored for evidence of clinically significant systemic irAE (e.g., systemic lupus erythematosus-like diseases) or organ-specific irAE (e.g., rash, colitis, uveitis, hepatitis or thyroid disease). If an irAE is noted, appropriate work-up (including biopsy if possible) should be performed, and steroid therapy may be considered if clinically necessary.

It is unknown if systemic corticosteroid therapy has an attenuating effect on ipilimumab activity. However, clinical anti-tumor responses have been maintained in patients treated with corticosteroids and discontinued from ipilimumab. If utilized, corticosteroid therapy should be individualized for each patient. Prior experience suggests that colitis manifested as \geq Grade 3 diarrhea requires corticosteroid treatment.

The most common immune-related adverse events are dermatologic, endocrine, gastrointestinal, and hepatic. For any suspected immune-related adverse event, begin with the algorithm in the Appendix. For diarrhea, hepatotoxicity, or endocrinopathy, this will refer the investigator to a more specific algorithm (see Appendix). For rash, see the below.

Skin related AE

Fatal toxic epidermal necrolysis (TEN) has been reported following a grade 3 skin-related AE, which was considered unrelated to ipilimumab on a Bristol-Myers Squibb-sponsored trial. In patients with a **drug-related** Grade 2 skin immune-mediated toxicity or Grade 3 skin-related adverse event, **regardless of causality**, additional treatment will be delayed until the event improves to \leq Grade 1 severity.

In patients with **drug-unrelated** grade 2 skin-related adverse events, no dosing delay is required. Patient with a Grade 1 skin AE, **regardless of causality**, are to be treated per institutional guidelines.

A dermatologist should evaluate persistent or severe rash or pruritus. A biopsy should be performed if appropriate and if possible, photos of the rash should also be obtained. Low grade ipilimumab-mediated rash and pruritus were treated with symptomatic therapy (e.g., antihistamines). Topical or parenteral corticosteroids may be required for more severe symptoms. With the appearance of any generalized rash, concomitant medications (e.g.. antibiotics, anticonvulsants, or proton pump inhibitors) that may be associated with severe skin reactions (e.g., Stevens Johnson Syndrome, TEN) should be discontinued and avoided. Ipilimumab should also be held.

Specific treatment algorithms for immune-related adverse events are included as appendices to this protocol.

5.4.6 Discontinuation of Ipilimumab Treatment

The following treatment-related non-neurological adverse events require permanent discontinuation of ipilimumab:

- Any \geq Grade 2 eye pain or reduction of visual acuity that does not respond to topical therapy and does not improve to \leq Grade 1 severity within 2 weeks of starting therapy, OR requires systemic treatment.
- Any \geq Grade 3 bronchospasm or other hypersensitivity reaction.

- Any other \geq Grade 3 non-skin related adverse event with the exception of events listed below under “Exceptions to Permanent Discontinuation”.
- Any \geq Grade 4 laboratory abnormalities, except AST, ALT, or Total Bilirubin
- AST or ALT $> 5 \times$ ULN
- Total Bilirubin $> 3 \times$ ULN
- Any other \geq Grade 4 adverse event
- *Withhold of ipilimumab for greater than 60 days due to treatment related toxicity*
- Any adverse event, laboratory abnormality or intercurrent illness, which, in the judgment of the investigator, presents a substantial clinical risk to the patient with continued dosing.
- The development of progression in the global tumor burden and/or clinical deterioration of subject’s condition such that further benefit from ipilimumab dosing is unlikely or requires a change of therapy.

The following neurological adverse event requires permanent discontinuation of ipilimumab and defines unacceptable neurotoxicity:

- Any motor neurologic toxicity \geq Grade 3 regardless of causality
- Any \geq Grade 3 treatment related sensory neurologic toxicity

Please refer to the Appendices for specific treatment algorithms.

5.4.6.1 Exceptions to Permanent Discontinuation

- Potentially reversible inflammation ($<$ Grade 4), attributable to a local anti-tumor reaction and a potential therapeutic response. This includes inflammatory reactions at sites of tumor resections or in draining lymph nodes, or at sites suspicious for, but not diagnostic of metastasis.
- Hospitalization for \leq Grade 2 adverse events where the primary reason for hospitalization is to expedite the clinical work-up.
- Patients with the following conditions where in the investigator’s opinion continuing study drug administration is justified:
 - Ocular toxicity that has responded to topical therapy.
 - Endocrinopathies where clinical symptoms are controlled with appropriate hormone replacement therapy. **Note:** Ipilimumab may not be restarted while the patient is being treated with systemic corticosteroids except for patients on stable doses of hormone replacement therapy such as hydrocortisone.

5.5 Prohibited Therapies During the Study

Patients in this study may not use vaccines for the treatment of cancer or prevention of disease unless indicated as a component of the protocol regimen (including those for common medical

conditions) for up to one month pre- and post-dosing with ipilimumab. Concomitant systemic or local anti-cancer medications or treatments are prohibited in this study while receiving ipilimumab treatments. Bone targeted agents (e.g. zolendronate, denosumab) are allowed.

Patients may not use any of the following therapies during the study:

- Any non-study anti-cancer agent (investigational or non-investigational)
- Any other investigational agents
- Any other (non-CA184024 related) CTLA-4 inhibitors or agonists
- Immunosuppressive agents
- Chronic systemic corticosteroids

Patients should receive full supportive care, including transfusions of blood and blood products, erythropoietin, antibiotics, antiemetics, etc., when appropriate. Treatment with hormones or other chemotherapeutic agents may not be administered except for hormones administered for non-disease-related conditions (e.g., insulin for diabetes mellitus) and continued LHRH agonist therapy. Palliative radiation therapy may not be administered during protocol treatment. No steroids, except as directed by the protocol, for immune events or for severe hypersensitivity reactions, are allowed.

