4.1 Inclusion Criteria

- 1) Histologically confirmed, metastatic prostate adenocarcinoma (positive bone scan and/or measurable disease on CT scan and/or MRI of the abdomen and pelvis).
- 2) History of progressive disease after androgen deprivation, defined by one OR both of the following:

- Objective radiographic progression defined by PCWG2³⁹ or RECIST criteria⁴⁰
- PSA evidence for progressive prostate cancer which consists of a PSA level of at least 2 ng/ml, which has risen on at least 2 successive occasions, at least 1 week apart. If the confirmatory PSA (#3) value is not greater (i.e., #3b) than the screening PSA (#2) value, then an additional test for rising PSA (#4) will be required to document progression (Figure 2).

3) If no prior orchiectomy has been performed, patients must remain on LHRH agonist or antagonist (e.g. degarelix) therapy. Patients who are receiving an antiandrogen as part of primary androgen ablation must demonstrate disease progression following discontinuation of the antiandrogen, defined as two consecutive rising PSA values, obtained at least two weeks apart, or documented osseous or soft tissue progression. At least one of the PSA values must be obtained at least four weeks (flutamide) or six weeks (bicalutamide or nilutamide) after discontinuation.

4) Laboratory requirements:

- Absolute neutrophil count (ANC) $\geq 1500/\mu\text{L}$
- Bilirubin $< 1.5 \times \text{ULN}$
- Hemoglobin $\geq 8 \text{ g/dL}$
- PSA $\geq 2 \text{ ng/mL}$
- Platelets $\geq 100,000/\mu\text{L}$
- AST and ALT $\leq 2.5 \times \text{ULN}$
- Creatinine clearance $\geq 60\text{mL/min}$ by the Cockcroft Gault equation: $(140 - \text{age}) \times \text{weight} (\text{kg}) / (\text{serum creatinine} \times 72)$
- Testosterone $\leq 50 \text{ ng/dL}$

- 5) Eastern Cooperative Oncology Group (ECOG) performance status 0 – 1 and life expectancy \geq 12 weeks.
- 6) At least 18 years of age or older.
- 7) Patients receiving any other hormonal therapy, including any dose of megestrol acetate (Megace), Proscar (finasteride), or any systemic corticosteroid, must discontinue the agent for at least four weeks prior to ipilimumab treatment. Progressive disease as defined above must be documented after discontinuation of any hormonal therapy (with the exception of a LHRH agonist).

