6.2 Procedures by Visit

6.2.1 Study Procedures by Visit and Treatment Cycle

Note that results of all safety laboratory tests (all chemistry and all hematology results) must be obtained and reviewed before ipilimumab administration, as applicable. All laboratory results must be within the established range before ipilimumab is administered. Laboratory evaluations using a local laboratory must be performed and the result examined by the investigator before administration of each dose of ipilimumab.

6.2.1.1 *Screening/Baseline Visit (within 15 days of Cycle 1 Day 1, unless otherwise indicated)*

- Informed consent (can occur any time pre-ipilimumab)
- Physical Exam including height, weight
- Medical history and concomitant medication review
- Performance Status evaluation
- Laboratory Tests: CBC with differential and platelets, serum chemistry (SGOT, SGPT, alk phos, total bili, LDH, electrolytes (Na, K, CO₂, Cl), glucose, BUN, Cr, amylase, lipase), PSA,
 - Within 28 days of Cycle 1 Day 1: Testosterone, TSH, free T4.
- Cortisol stimulation test
- Urinalysis with micro (within 28 days of Cycle 1 Day 1)
- CT abdomen/pelvis with contrast and Bone Scan (within 8 weeks of Cycle 1 Day 1)
- Archived tumor tissue (if available)
- Immune monitoring – all patients at UCSF and MD Anderson (can occur any time after signing consent)
- Immune worksheet

6.2.1.2 *Treatment Visits*

All patients will receive SipT treatment (leukapheresis and infusion) every 2 weeks. The leukapheresis and infusion appointments are scheduled 2 to 3 days apart, and can start on various days of the week. The final infusion dose of SipT (Day 0) is usually about 30 days from the date of first dose.

All patients will receive ipilimumab 3 mg/kg IV on Day 1 of each 21-day cycle. Laboratory assessments listed below may be performed +/- 3 days from Day 1 in order to allow for the collection and review of results prior to dosing.

Day 1 of Induction Cycles 1-4 (+/- 3 days)

Pre-study clinical physical exam, performance status, and laboratory parameters, including Immune Monitoring, are to be measured within 15 days of beginning treatment and do not need to be repeated on Cycle 1 Day 1.

- Physical Exam, including weight
- Toxicity and concomitant medications assessment
- Performance Status assessment
- Laboratory Tests: CBC with differential and platelets, serum chemistry (SGOT, SGPT, alk phos, total bili, LDH, electrolytes, glucose, BUN, Cr, amylase, lipase), PSA

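### Section 4.1 item 3 requires men on an LHRH antagonist to stay on it, but section 5.5 exempts only LHRH agonists from the hormone ban, so both rules cannot be followed

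*Combined protocol and SAP*

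**What the plan says.** Three places in the combined protocol and SAP deal with background LHRH therapy.

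- **Section 4.1, item 3.** For men without orchiectomy, "patients must remain on LHRH agonist or antagonist (e.g. degarelix) therapy". Both drug classes are covered, an antagonist is named, and continuation is mandatory.
- **Section 4.1, item 7.** Men on *other* hormonal therapy (megestrol, finasteride and systemic corticosteroids are the examples) must stop it at least four weeks before ipilimumab. Progression must be documented "after discontinuation of any hormonal therapy (with the exception of a LHRH agonist"; the parenthesis closes there, with no mention of antagonists.
- **Section 5.5.** The on-study rule bars hormone treatment "except for hormones administered for non-disease-related conditions (e.g., insulin for diabetes mellitus) and continued LHRH agonist therapy". These are the only two exemptions. The same section also lists as barred "Any non-study anti-cancer agent (investigational or non-investigational".

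Testosterone must be no higher than 50 ng/dL at entry (section 4.1, item 4). It is scheduled once, at screening: "Within 28 days of Cycle 1 Day 1: Testosterone, TSH, free T4" (section 6.2.1.1). The study calendar in section 6.1 marks no later test.

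**The concern.** Item 3 and section 5.5 are both operative rules, and for a man on an antagonist they give opposite instructions. The two centres could settle this differently, one continuing the drug and recording a deviation, the other stopping it.

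If the drug were stopped, the castrate state required at entry might be lost during follow-up. The PSA definitions in section 7.1.3.1 do not require castration to be maintained. A confirmed rise of 25% and at least 2 ng/mL counts as PSA progression in a man without a 50% decline, and PSA progression alone is enough for progressive disease. For that man, PSA decline, time to PSA progression and time to progression could partly reflect lost androgen suppression instead of the study treatment.

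**Working it through.** **1. Can an antagonist user satisfy every rule?**

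| Place | LHRH agonist | LHRH antagonist |
|---|---|---|
| 4.1 item 3 | must continue | must continue |
| 5.5 hormone ban | exempt | not exempt |
| 4.1 item 7, parenthesis | exempt | not named |

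The first two rows conflict in the antagonist column. The exemption for non-disease-related hormones does not help, because the antagonist is given for the prostate cancer. The third row repeats the omission but is not a clear conflict, because item 7 begins with *other* hormonal therapy.

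**2. Would an interruption be seen?** By testosterone, no: the only scheduled test is at screening. By concomitant medication, possibly: sections 6.1, 6.2.1.2 and 6.2.1.3 schedule that review at days 22, 43, 64 and 85, at follow-up visits and off study.

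**3. Which endpoints depend on it?** The primary endpoint is IgG response at week 20, tested within each arm against 15% (sections 9.1.2 and 9.3.1.2). The stated design reproduces. With n = 27 and rejection at 9 or more responders, P(X ≥ 9 | 0.15) = 0.0138, which is below 0.025. Power is P(X ≥ 9 | 0.40) = 0.816, against the stated 81%. The castration rule enters neither figure. The PSA and progression endpoints are secondary and are summarised descriptively by arm (section 9.3.2.1).

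**4. How large could it be?** The documents give no share of antagonist users, so a share f is assumed, from 2% to 30%.

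- Antagonist users per arm: 27 × 0.02 = 0.5 to 27 × 0.30 = 8.1.
- One changed PSA outcome: 1/27 = 3.7 percentage points in that arm.
- Worst case, in which every antagonist user is taken off therapy and none can then show a PSA response: observed rate = p × (1 − f).

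| Assumed true PSA response p | f = 2% | f = 30% |
|---|---|---|
| 20% | 0.20 × 0.98 = 19.6% | 0.20 × 0.70 = 14.0% |
| 30% | 0.30 × 0.98 = 29.4% | 0.30 × 0.70 = 21.0% |

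If every site follows item 3, no PSA value changes, and the only consequence is a therapy given against section 5.5.

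**The case against.** The best defence is that sites would not stop castration on the strength of section 5.5. Item 3 is the more specific rule: it names an antagonist and says patients must remain on it. Section 7.3.2 excludes toxicity attributable to androgen deprivation from significant adverse events without distinguishing the classes, so the protocol expects such therapy on study. Section 5.5 is loosely drafted: its bar on non-study anti-cancer agents, read literally, would catch the agonists that the same section allows. The likelier outcome is that the antagonist continues and a deviation may be recorded.

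This stands as a limit on the consequences. It does not remove the conflict, because item 3 itself separates the two classes, so *agonist* in 5.5 cannot safely be read as covering both.

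Three stronger readings are tempting and are not supported:

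- **Item 7 makes antagonist users stop and then progress.** After item 3, *other* most naturally means therapy beyond the background LHRH treatment. An agonist-only exemption does leave room for doubt, but that supports tidying the parenthesis, not a claim that the item orders the drug stopped.
- **The PSA endpoints are corrupted.** Only men actually taken off therapy could be affected. A PSA rise from lost suppression would count against apparent activity; it would not create false responses.
- **Reinduction would be triggered falsely.** Section 3.3 requires a clinical response in the first 12 weeks before later progression. Early loss of castration would tend to prevent eligibility.

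**Conclusion.** The contradiction between section 4.1 item 3 and section 5.5 is real and is visible from the text alone: a man on an antagonist cannot comply with both. The item 7 parenthesis shares the omission but adds no clear conflict of its own.

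The statistical reach is small. It covers antagonist users only, and among them only those whose therapy is interrupted, and it touches secondary descriptive endpoints. Both arms are under the same wording and randomization is stratified by site (section 3.2), so nothing in the rule favours one arm.

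The worst-case loss, from an observed 30% to 21%, rests on three assumptions that the documents do not supply: a 30% antagonist share, every such man taken off therapy, and none of them able to respond. It is an outer bound, not an expectation. This is a drafting inconsistency that should be corrected, not a flaw in the primary analysis.

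**What to change.** Reconcile section 5.5 and the parenthesis in section 4.1 item 7 with section 4.1 item 3, so that all three treat the same background LHRH therapies in the same way. Which therapies are required, allowed or exempted is for the sponsor to decide; this review takes no position on it.

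The cost is a few words in two places. Under section 10.5 the change needs an amendment with IRB approval, so it can go with the next one. No change to sample size, visits or analysis follows. For men already treated, the concomitant-medication records could be checked for antagonist use and any interruption, which would show whether any PSA outcome is affected.

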6 STUDY PROCEDURES AND OBSERVATIONS

The Study Calendar summarizes the frequency and timing of various measurements.

6.1 Study Calendar

Evaluation or Treatment	Pre-study			Pre- Ipilimumab	Treatment					Follow Up	
	Proven ge 1	Proven ge 2	Proven ge 3		Day 1 ^a +/- 3 days	Day 22 +/- 3 days	Day 43 +/- 3 days	Day 64 +/- 3 days	Day 85 +/- 3 days	Monthly for 3 months, then Q3 months ⁱ	Off Study
Arm 1: Immediate Ipilimumab^b					X	X	X	X			
Sipuleucel-T	X	X	X								
Arm 2: Delayed Ipilimumab^b						X	X	X	X		
Sipuleucel-T	X	X	X								
Informed Consent				X							
Physical Exam				X		X	X	X	X	X	X
Medical History				X							
Height				X							
Weight				X		X	X	X	X	X	X
Concomitant Medications				X		X	X	X	X	X	X
Toxicity Assessment				X		X	X	X	X	X	X
Performance Status				X		X	X	X	X	X	X
CBC w/diff, platelets				X		X	X	X	X	X	X

6.1 Study Calendar

Evaluation or Treatment	Pre-study			Treatment					Follow Up		
	Proven ge 1	Proven ge 2	Proven ge 3	Pre- Ipilimum ab	Day 1 ^a +/- 3 days	Day 22 +/- 3 days	Day 43 +/- 3 days	Day 64 +/- 3 days	Day 85 +/- 3 days	Monthly for 3 months, then Q3 months ⁱ	Off Study
Serum chemistry^c				X		X	X	X	X	X	X
PSA				X	X	X	X	X	X	X	X
Urinalysis w/ micro				X		X	X	X	X		
Testosterone				X							
TSH, free T4				X	X	X	X	X	X	X	X
Blood for immune monitoring (all patients)^d				X	X ^j	X	X	X	X	X	X
CT/MRI & Bone scan^{f, g}				X ^e					X	X	
Immune Worksheet^h				X	X	X	X	X	X	X	X
Cortisol stimulation test				X							
Archived tumor tissue (if available)				X							

^a. Pre-study clinical (physical exam and performance status) and laboratory parameters are to be measured within 15 days of beginning treatment (unless otherwise indicated in section 6.2.1.1) and do not need to be repeated on Day 1.

^b. Patients randomized to Arm 1 will begin treatment with Ipilimumab 1-3 business days following the last Provenge infusion. Day 1 of the trial will be designated as the day the patient receives the first dose of ipilimumab. For patients randomized to Arm 2, Day 1 will be determined following the same parameters as Arm 1 (1-3 business days following the final Provenge infusion), with Day 22 designated as the day the patient receives the first dose of Ipilimumab

^c. SGOT, SGPT, alk phos, total bili, LDH, electrolytes (Na, K, CO₂, Cl), glucose, BUN, Cr, amylase, lipase.

^d. 60 mL in a green top tube will be collected from all patients and shipped/delivered by the Clinical Research Coordinator to [name] laboratory ([name]) for the ELISA and ELISPOT immune assays. Blood must be drawn pre-treatment. Please refer to the Lab Manual for shipping instructions for blood.

- e. Pre-study radiographic staging is to be measured within 8 weeks of beginning treatment.
- f. CT/MRI abd/pelvis is at baseline. If metastatic disease is suspected elsewhere, other imaging modalities (e.g. CT chest) are accepted to demonstrate progressive disease for eligibility. This imaging should continue with protocol-required scans throughout study participation, as indicated. If soft tissue metastatic disease is found at baseline, scans will be repeated at day 85 (+/- 7 days) and every 12 weeks (+/- 7 days) thereafter. Can also be done more often if clinically indicated.
- g. Bone scans are at baseline, day 85 (+/- 7 days), and every 12 weeks (+/- 7 days) until PD is reached; can be more often if clinically indicated.
- h. Every Clinic visit will include clinical monitoring for clinical autoimmunity as outlined in Appendix 2.
- i. Q3month follow-up visits should continue until PD or 2 years, whichever comes first.
- j. Blood for Immune Monitoring does not need to be repeated on Day 1 if drawn within 15 days of Day 1.

6.2 Procedures by Visit

6.2.1 Study Procedures by Visit and Treatment Cycle

Note that results of all safety laboratory tests (all chemistry and all hematology results) must be obtained and reviewed before ipilimumab administration, as applicable. All laboratory results must be within the established range before ipilimumab is administered. Laboratory evaluations using a local laboratory must be performed and the result examined by the investigator before administration of each dose of ipilimumab.

6.2.1.1 *Screening/Baseline Visit (within 15 days of Cycle 1 Day 1, unless otherwise indicated)*

- Informed consent (can occur any time pre-ipilimumab)
- Physical Exam including height, weight
- Medical history and concomitant medication review
- Performance Status evaluation
- Laboratory Tests: CBC with differential and platelets, serum chemistry (SGOT, SGPT, alk phos, total bili, LDH, electrolytes (Na, K, CO₂, Cl), glucose, BUN, Cr, amylase, lipase), PSA,
 - Within 28 days of Cycle 1 Day 1: Testosterone, TSH, free T4.
- Cortisol stimulation test
- Urinalysis with micro (within 28 days of Cycle 1 Day 1)
- CT abdomen/pelvis with contrast and Bone Scan (within 8 weeks of Cycle 1 Day 1)
- Archived tumor tissue (if available)
- Immune monitoring – all patients at UCSF and MD Anderson (can occur any time after signing consent)
- Immune worksheet

6.2.1.2 *Treatment Visits*

All patients will receive SipT treatment (leukapheresis and infusion) every 2 weeks. The leukapheresis and infusion appointments are scheduled 2 to 3 days apart, and can start on various days of the week. The final infusion dose of SipT (Day 0) is usually about 30 days from the date of first dose.

All patients will receive ipilimumab 3 mg/kg IV on Day 1 of each 21-day cycle. Laboratory assessments listed below may be performed +/- 3 days from Day 1 in order to allow for the collection and review of results prior to dosing.

Day 1 of Induction Cycles 1-4 (+/- 3 days)

Pre-study clinical physical exam, performance status, and laboratory parameters, including Immune Monitoring, are to be measured within 15 days of beginning treatment and do not need to be repeated on Cycle 1 Day 1.

- Physical Exam, including weight
- Toxicity and concomitant medications assessment
- Performance Status assessment
- Laboratory Tests: CBC with differential and platelets, serum chemistry (SGOT, SGPT, alk phos, total bili, LDH, electrolytes, glucose, BUN, Cr, amylase, lipase), PSA
- Immune monitoring – all patients at UCSF and MD Anderson
- Additional immune monitoring – MD Anderson patients ONLY
- TSH, T4 (beginning at Cycle 2 Day 1 – Study Day 22)
- Urinalysis with micro
- Immune worksheet

Bone scans will be performed every 12 weeks during induction treatment, or when clinically indicated, and at disease progression. CT scans will be performed every 12 weeks only if baseline scan is indicative of metastatic disease; or if otherwise clinically indicated.

